Audio recordings of interviews will not include the respondent's name or demographic information, and will be identified only by the participant's numeric study ID. Additionally, all audio recordings will be deleted following transcription. During the transcription process, any identifying information that was incidentally revealed during the interview will be left out of the record. If audio recordings need to be shared among the research team to facilitate transcription, a secure file sharing service will be used. If a given recording happens to contain identifying information, only VA-credentialed researchers will be provide access to it.

Daily breathalyzer responses will be texted to the interventionist's study phone from the participants. On a weekly basis, the interventionist will transfer these readings to a secure database housed on a password-protected computer and delete them from her mobile device. Participants will be provided guidance (in the form of a handout) about how to delete the readings from their own phones (or the study phones).

Local computers containing research data will be password protected and encrypted using either FileVault (Mac) or BitLocker (Windows). If research files are shared among the research team, an encrypted file sharing service will be used.

Data security Plan

All questionnaire-based assessments, including the post-session questionnaires for the open trial, the baseline and follow-up assessments for both the open trial and the intervention, and the surveys used for daily self-monitoring for the open trial and intervention, will be delivered in an electronic format. The surveys will be programmed and delivered using Qualtrics, which houses data and responses on a secure, password-protected site.

For questionnaires completed in the clinic, the tablets will be pre-loaded with links to the online surveys. For surveys conducted via mobile phone, participants will be texted a link to the assessments, which they can then open and complete using a mobile browser. At the beginning of the survey, participants will enter a unique identifier assigned to them at enrollment, which they can ask the interventionist for at any time in case they forget. Any data files containing contact information and identifiers will be kept separate from the survey responses on a secure, password-protected computer. Following the completion data collection, identifying information will be permanently removed from all electronic files. Participants will be trained regarding how to secure their mobile phone using a password, and the mobile phone used by the counselor will also be secured.

The interviews following the open trial will be conducted only by researchers affiliated with the project and not by individuals working at the VA. Responses will be recorded digitally. Recordings will then be transcribed by a research assistant and any identifying information will be removed, with pseudonyms used if necessary. Following the transcription of all files, which will be kept on password-protected computers, the recordings of the interviews will be deleted. The transcripts will be stored with all other research data and kept for 6 years before being destroyed.

The twice-daily self-monitoring completed by participants involves breathalyzer readings collected via text message. Each phone will be pre-loaded with contact information for the study coordinator's dedicated cell phone to reduce any chances of confusion or sending the information to the wrong individual. Both the participants' and coordinator's phones will be secured using a password, and coordinators will manually upload readings to a computer using a USB cable. After they are uploaded, the coordinator will delete readings from their phone. Study phones will likely be used by multiple participants throughout the rolling enrollment procedure of the intervention, so each phone will undergo a factory reset to avoid compromising any previous participants' data. This will not be necessary if participants choose to use their own phones for the study.

To protect against loss of confidentiality, we will follow strict data management procedures. Access to data will be permitted only to the researchers and counselors, who will be trained in HIPAA procedures and will sign confidentiality agreements. Any contact information will be stored separately from responses and permanently deleted following the completion of data collection. Consent and HIPAA Authorization forms, which will be the only physical forms with identifying information, will be kept in a locked file cabinet in the coordinator's office. Moreover, members of the research team (e.g., research assistants) will be required to participate in training in the areas of ethics, confidentiality protection, and human subject participants. They will also be trained on a protocol regarding how to avoid identifying research participants who are seen out of the research setting.

To secure data on mobile phones, respondents will be taught how to delete messages or photos if they are worried about their information being compromised. Both respondents and counselors will be trained regarding and required to secure their phone using a password. A web-based service that allows complete control over data will be chosen to deliver the self-monitoring reminders, and any data collected during this process will be downloaded to a secure computer and deleted from the website following the completion of data collection. Finally, all phones will be capable of being remotely wiped in the case of loss or theft to protect participants' information. After each participant concludes with the intervention, the phone will undergo a factory reset to remove any traces of data or identifying information. Together, these steps are more than adequate to minimize and protect against risk.

6. Potential benefits/risks

Participants in the proposed research will benefit primarily by receiving free alcohol reduction counseling, which has potential to not only reduce their alcohol use, but improve their HIV medication adherence and, in turn, their overall health. The self-monitoring aspect will also increase their own awareness of their behaviors and potentially improve their ability to recognize contextual predictors that encourage alcohol use or a lack of medication adherence. Finally, participants will receive financial compensation for their participation. All participants will receive these benefits with minimal effort, as the intervention requires few in-person visits, while the rest can be received via mobile phone.

For all participants, there is the potential risk of anxiety or discomfort when reporting opinions or receiving educational intervention content. The interviews and surveys will address sensitive information or information that may cause embarrassment, such as substance use behaviors and mental health status. Additionally, there is also the risk of loss of confidentiality, as identifying information will be collected in order to monitor participants' data throughout the course of the planned research, as well as to obtain their HIPAA authorization.

There are also inherent risks in using communication technologies for delivering a health intervention. The videoconferencing sessions of the intervention will occur over a HIPAA-compliant secure network, so they will pose no risk. However, any of the activities done using mobile phones, including intervention sessions and self-monitoring, are inherently less secure. Participants and study personnel will receive thorough training on how to secure their mobile phones to prevent any unauthorized access to data, and each phone will have the potential to be remotely wiped in case of theft or loss. The study coordinator will explain this issue carefully and get consent of understanding as part of the study protocol.

In the event that identifying information is released to an unauthorized party, the serostatus of participants could be revealed to unwanted individuals. This could potentially cause harm, but is unlikely considering the careful plans in place regarding data management and protection. All possible measures will be taken to protect information provided through surveys, interviews, and intervention participation, and confidentiality will be respected. Following completion of data collection, responses will become anonymous as identifying information is permanently deleted. For these reasons, we estimate that this minimally-invasive project poses minimal risk.

STATISTICAL ANALYSIS PLAN

For the randomized controlled trial, data analytic methods will be focused on examining acceptability and feasibility, as well as effects on alcohol intake, HAART adherence, and HIV-related medical outcomes (CD4 count and viral load). Intervention adherence, daily monitoring adherence, and session acceptability will be described using descriptive statistics. Session attitudes will be assessed using several 5-point semantic differential attitudinal measures rating the session, including Boring/Interesting, Unpleasant/Pleasant, Bad/Good, Useless/Useful, and Negative/Positive. Scores on the session attitude semantic differential measures will be reverse-coded where required and averaged to form an overall attitude score, with “0” being “neutral.”

We will provide descriptive summaries for the outcome variables, including mean, median, and standard deviation for continuous variables and counts and percentages for categorical variables. We will summarize the outcome variables overall and across the intervention groups. In assessing the differences in alcohol use and medication adherence between the two groups during the 8-week intervention period, we will utilize the Kruskal–Walli’s test, a non-parametric statistical approach, to compare the distribution of outcome variables. The general linear model (ANOVA) will be used to estimate the difference between alcohol use and medication adherence among the groups, and the estimation of the effect size (Cohen’s D) at the end of the 8-week intervention period. While this study was not powered to detect significant differences, the goal of these analyses is to observe changes and effect sizes that may provide preliminary evidence of efficacy.

To examine intervention effects as assessed through daily surveys, we will examine responses to the morning survey question asking if participants had consumed alcohol on the previous day (yes/no), whether or not they reported a positive breathalyzer reading (> 0.0), and if they had taken all of their HAART on the previous day (yes/no). Within the 8-week intervention period and using the daily data, we will assess the change in the proportion of participant's alcohol use, the proportion of positive breathalyzer readings, and the proportion of their medication use from the beginning of week 1 to the end of week 8 using McNemar's matched pair test. This test will allow us to address the interdependency in the repeated measurements. We will account for missing survey responses by considering two scenarios: First, assuming they were missing completely at random and remained missing, and second, that missing values were indicative of alcohol use/medication nonadherence and were thus filled in as drinking days/positive breathalyzers/nonadherent days (a conservative approach).

All participants will have received the intervention by the end of the 8 week (2-month) post-intervention period. To examine long-term intervention effects, participants from both the waitlist-control and intervention group will be combined into a single dataset. A generalized linear model (via SAS GENMOD PROCEDURE) and a multiple linear regression model will be fit to the change from baseline for each outcome measure. Change from baseline is the difference between the baseline value and values obtained at subsequent time points: 8 weeks (immediate post-intervention; T2 for intervention group and T3 for waitlist-control), and 16 weeks (2 months post-intervention; T3 for intervention group and T4 for waitlist-control) for each outcome measure. The rationale for fitting the change from baseline is that this model removes the effect of baseline differences that may exist from the model. All statistical hypothesis tests will be conducted using the standard 5% significance level. SAS Version 9.4 (TS1M1, SAS Institute, Cary, NC), will be used for all analyses.

References

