The counselor will stick to a pre-written script in delivering the intervention content, while also allowing for some time to discuss the participant’s drinking behavior over the past week and address any questions the participant might have. In addition to receiving the eight sessions of intervention content, participants will complete smartphone-based self-monitoring of medication adherence and alcohol consumption, which will be discussed during intervention sessions. Each day, they will be texted at two random times to complete a breathalyzer reading using a BACtrack Mobile Pro, which is sold by a company with FDA clearance and utilizes law enforcement-grade sensors for determining blood alcohol level. It connects wirelessly to phones via Bluetooth, automatically uploads readings, allows the user to view their current and past readings with a mobile app, and allows them to share their readings with counselors. At the time of the breathalyzer reading, participants will also be asked to indicate via survey how many drinks they have consumed and their medication use for the day. During intervention sessions, the counselor will discuss the patients’ alcohol use reports from the previous week.

Study Procedures/Evaluations

Step 1: Patient recruitment and screening (Goal=50 patients total)

1. Three weeks ahead of patient medical visits, the VA research coordinator will send out a letter detailing the study information and informing the patient that they will have a chance to learn more and/or enroll at their next medical appointment
2. One week before the appointment, the VA coordinator will call the patients to tell them about the study and inform them that they will have a chance to enroll during their next appointment (see recruitment script)
3. Following a medical visit at the VA clinic, patients will be offered the chance to speak to the research coordinator about the study
4. The research coordinator will briefly explain the study (see recruitment script) to the patient.
5. If the patient is interested, they will be given a tablet to complete a screening assessment.
 - a. Alternatively, the patient may elect to complete the screening assessment over the phone at a later time
6. The screening assessment will examine:
 - a. Risky drinking behavior
 - b. Medication adherence (single item asking about percentage of doses taken within the previous month)
 - c. Age
 - d. HIV status

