7. The research coordinator will check to see if the following inclusion criteria are met:
 - a. HIV-positive
 - b. 18 years or older
 - c. An at-risk drinker as identified by the alcohol screener
 - d. Currently taking HIV medication
 - e. A score less than 20 on the AUDIT questionnaire
 - i. Score is displayed on the final page of the questionnaire. If above 20, see step 9 below for further direction.
8. If patients are eligible, the research coordinator will provide them with a TRAC flyer and consent form
 - a. If the patient wants to enroll in the study, the coordinator will proceed with enrollment (see next section)
 - b. If the patient does not want to enroll today, they can take the TRAC flyer and consent form with them. If they want to enroll at a later date, they can call the VA coordinator.
 - c. They are eligible to begin the study if they enroll within 30 days. If they would like to join the study after that date, they will need to be re-screened.
9. If patients are ineligible because of a score of 20 or higher on the AUDIT questionnaire, a note will be made in their chart and a referral made to their clinical team for follow-up regarding concerning levels of alcohol use.
10. Screening activities will not collect any data to be used in the study.

Step 2: Patient Enrollment

1. The coordinator will go through the consent form and HIPAA form with the participant, discussing:
 - a. The overall purpose of the study
 - b. The time commitment of the study
 - c. Their expectations as a participant
 - d. The incentives they will receive
 - e. Any questions the participant has
2. Once the participant has demonstrated sufficient understanding of the consent and HIPAA forms, the research coordinator will obtain consent and a signature on the HIPAA form.
3. The research coordinator will assign the participant a numeric identifier and record it in the secure code key
 - a. The research coordinator will inform the participant that if they forget their study ID at any time, they can contact the researchers to learn what it is.
4. Only researchers will have access to this key, which will be kept in a password-protected file

5. The research coordinator will then check the randomization spreadsheet (pre-generated set of random numbers for each participant ID assigning them to the intervention or waitlist-control group)
 - a. If they are in the intervention group (Group 1):

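### No allocation concealment is described: as written, the coordinator who enrols patients could see upcoming assignments, or choose an ID, before enrolling the next patient

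*Combined protocol and SAP*

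**What the plan says.** Protocol section 4 sets out enrolment step by step and gives the successive tasks to one role.

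- Recruitment (Step 1, item 4): "The research coordinator will briefly explain the study (see recruitment script) to the patient".
- Eligibility (Step 1, item 7): "The research coordinator will check to see if the following inclusion criteria are met".
- Consent (Step 2, item 2): "the research coordinator will obtain consent and a signature on the HIPAA form".
- Identifier (Step 2, item 3): "The research coordinator will assign the participant a numeric identifier and record it in the secure code key".
- Allocation (Step 2, item 5): the research coordinator is then to "check the randomization spreadsheet (pre-generated set of random numbers for each participant ID assigning them to the intervention or waitlist-control group".

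The one access rule in this sequence is Step 2, item 4: "Only researchers will have access to this key, which will be kept in a password-protected file". It concerns the code key that links IDs to people, not the randomization spreadsheet.

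The documents do not state an allocation ratio, blocking, who generated the list or who keeps it. The data security plan and the SAP do not mention concealment. The section on protocol deviations for COVID-19 has the interventionist go through the consent documents by phone and does not describe randomisation.

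**The concern.** Concealment means that whoever decides whether and when a patient enters cannot know which arm that patient will get. Here the ID fixes the arm, and the person enrolling the patient gives out the ID and reads the list. Two routes to selection are left open. Once the file has been opened for one participant, the arms of later IDs may be readable before the next patient is approached. And with no rule on the order of IDs, choosing an ID could mean choosing an arm.

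Steering would need no bad faith. The arms differ visibly (counselling now, or after an 8-week wait). Before allocation the coordinator checks the AUDIT result, and the screener also asks about medication adherence, so information related to outcome is close at hand. It would be natural to want a needier or keener patient to start at once.

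At stake is the comparison of alcohol use and medication adherence at the end of the first 8 weeks. It is the trial's only contrast with untreated controls, because the waitlist group then starts the intervention. The SAP concedes that power is lacking and presents the effect size as early evidence of efficacy, so a biased Cohen's d would affect one of the trial's main products. The SAP states no baseline covariate for this comparison, and measured covariates would not in any case capture motivation.

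**Working it through.** **Reading the procedure.** The plan has no figure to reproduce. The check is who does what, in which order, and what protects the list.

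1. The written order for each participant is consent, then ID, then look-up. For the current patient, the look-up therefore follows consent.
2. The list is prepared in advance and covers participant IDs in general. Concealment must protect the next allocation as well as the current one. Consent-before-look-up does not do that if the same person returns to the same file for each patient.
3. I looked for a safeguard in Steps 1 to 3, the COVID-19 section, the data storage and security sections and the SAP. None mentions an independent list holder, central release, sealed envelopes, masked rows, an access log or sequential ID issue.
4. Advance visibility is thus an inference from a stated procedure with no stated protection. It is not something the documents assert.

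**Which analyses are exposed (SAP).**

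- Week-8 Kruskal-Wallis test, ANOVA and Cohen's d: between arms, so exposed.
- McNemar tests on daily data: each participant against himself or herself, so not exposed through allocation.
- Long-term models: both groups combined and change from baseline modelled, so not exposed through allocation.
- Feasibility and acceptability: descriptive.

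**Size, as an illustration.** Inputs: N = 50 (protocol section 3). I assume 25 per arm, because no ratio is stated, and I assume that k patients who are 1 SD higher on the outcome trade places with k average patients, all in one direction.

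- Shift in each arm mean: k/25 SD, up in one arm and down in the other.
- Shift in d: 2k/25.
- Standard error of d near zero: sqrt(1/25 + 1/25) = sqrt(0.08) = 0.28.

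| Trades k | Patients misplaced (2k) | Shift in d (2k/25) | Shift / SE |
|---|---|---|---|
| 1 | 2 | 0.08 | 0.28 |
| 2 | 4 | 0.16 | 0.57 |
| 3 | 6 | 0.24 | 0.85 |
| 5 | 10 | 0.40 | 1.41 |

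The result hardly depends on equal arms. With 20 and 30, the shift for k = 3 is 3 × (1/20 + 1/30) = 0.25 and the standard error is sqrt(1/20 + 1/30) = 0.29.

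**The case against.** A reader might infer that randomisation was in fact unconcealed, that the coordinator keeps the list, or that each arm is known before consent. The documents do not go that far. They say the coordinator checks the spreadsheet, after consent and ID assignment. They do not say who keeps it or whether the whole list can be seen at once. An undocumented lock or a sequential-ID habit cannot be excluded. This limits the claim to what the procedure as written would allow.

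A reader might also take the 30-day window as proof that the coordinator can time enrolments to a slot. The text says "If they want to enroll at a later date, they can call the VA coordinator", which puts the timing with the patient, and the letters, calls and offers in Step 1 follow the appointment schedule. The other recruitment routes listed in section 4 leave some discretion, but the window is not evidence of control.

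The motive is limited too. Waitlist participants get the same intervention from week 8, and patients scoring 20 or more on the AUDIT are excluded, which narrows the range of need. That outcomes are self-reported bears on reporting after the arm is known, not on steering at allocation.

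On size, three trades misplace 6 of 50 patients in one direction at a full SD each, and even that shifts d by less than one standard error. One trade gives only 0.08. This stands, and it is why a range is shown. But sampling error is reported with the estimate, whereas selection bias is not and would go unnoticed.

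The one-role finding applies to the standard procedure only. Under the COVID-19 route the interventionist handles the consent discussion.

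**Conclusion.** The point holds as a gap in described concealment. In the standard procedure one role recruits, checks eligibility, takes consent, assigns the ID and reads the ID-to-arm list, with no stated safeguard and no rule on the order of IDs. No selection is shown to have occurred.

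The consequence is confined to the week-8 between-arm comparison. Under the assumptions above (25 per arm, a 1 SD difference within each traded pair, all trades in one direction) the bias in d runs from 0.08 for one trade to 0.40 for five. These are scenarios, not estimates. The change should be made: the remedy is cheap, and the exposed effect size is the pilot's only randomised evidence against untreated controls.

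**What to change.** - **Step 2, item 3:** state that IDs are issued in strict sequence at consent.
- **Step 2, item 5:** state that the allocation list is held by an existing team member who neither recruits nor treats. That person releases one assignment at a time, with the time logged, only after consent and eligibility are recorded. Sequentially numbered, sealed, opaque envelopes prepared by such a person are an acceptable alternative.
- **COVID-19 remote route:** apply the same release step and say where in the sequence it falls. The interventionist both discusses consent and treats, so should not hold the list.
- **If a safeguard already exists:** describe it in one sentence in Step 2.
- **If enrolment is under way or complete:** an amendment cannot repair past allocations. Compare ID order with consent dates, and report who had access to the list and how allocation was handled.

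The cost is protocol wording, access control on one file and a short wait at each of 50 enrolments. The protocol's data storage section shows team members at two universities; that one of them is free of recruiting and treating duties is an assumption to confirm. This change does not address the viral-load check in Step 2, item 5, which differs by arm and comes after the arm is known. That needs separate consideration.
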